## **5        SELECTION OF PARTICIPANTS AND STUDY ENROLLMENT AND WITHDRAWAL**

This study will screen approximately 600 women 18-55 years of age who have recurrent RBV, defined as a current BV infection and at least two previous episodes of BV by documentation or self-report in the past year. Women who meet Screening eligibility will be treated with a standard course of oral metronidazole or another CDC-recommended BV treatment. Participants will return within approximately one week of completing the metronidazole treatment or other CDC-recommended BV treatment, for assessment of clinical cure. Clinical cure of BV is defined as  $\leq 2$  of 4 Amsel criteria and absence of reported symptoms of BV (i.e. no malodorous discharge consistent with BV).

Participants who return for the Enrollment Visit, V1 and are determined to be clinically cured will be offered to review and sign the Enrollment consent. Participants who consent and meet Enrollment eligibility will be randomized in a 1:1 ratio to twice weekly blinded suppressive therapy with TOL-463 or placebo. It is estimated that approximately 250 participants will be eligible for Enrollment with approximately 125 participants in each suppressive therapy group.

No exemptions will be granted on Screening or Enrollment eligibility criteria for this DMID-sponsored trial.

Participants will be recruited from health clinics in the U.S.

Those participants who enroll in the study will undergo up to 3 scheduled Follow-up visits to evaluate clinical diagnosis of BV at each visit. Participants who develop vaginal symptoms between scheduled visits will be asked to return for an unscheduled visit. If at any time during a follow-up visit a participant is diagnosed with clinical BV ( $> 2$  Amsel criteria), the study endpoint of BV reoccurrence is met, and participation in the study will end.

The study will target a total of 200 evaluable participants.

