- Participants who are negative for BV determined as  $\leq 2$  of 4 Amsel criteria will be scheduled for the next return visit, blinded IP and a memory aid will be provided as needed, and protocol requirements and dosing instructions reviewed.

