### **7.1.1 Assessment of Concomitant Medications/Treatments other than Study Product**

Administration of any medications, therapies, or vaccines will be recorded on the appropriate DCF. Concomitant medications will include all medications taken 30 days prior to the initial screening visit V0, through V4 or early termination, whichever occurs first. Prescription and over-the-counter drugs will be included, as well as herbs, vitamins, and supplements.

Participants who have received study IP and are subsequently diagnosed with a concomitant infection that requires systemic antibiotics will receive treatment according to the local clinic's standard protocols but will be considered non-evaluable for efficacy and terminated from the study. However, participants who have received study IP and are subsequently diagnosed with VVC can remain in the study and be considered evaluable for efficacy if they are appropriate candidates for oral fluconazole therapy.

---

At the discretion of the site PI, use of new medication should prompt evaluation for the presence of a new diagnosis of chronic medical disease or condition.

Medications that might interfere with the evaluation of the IP should not be used unless absolutely necessary.

Refer to [Section 5](#) (Selection of Participants and Study Enrollment and Withdrawal) for medications that are prohibited for study eligibility and throughout study participation.

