4.5. Efficacy (Immunogenicity) and Safety Variables

Multiple observations within specific visit period are acceptable. In the case of multiple observations within a specific window, the assessment value that is closest to the scheduled visit window will be used in the analyses for the post-baseline records. Whether to use and how to use the observations from early termination at an unscheduled visit along with the observations obtained at the corresponding scheduled visit will be specified in the applicable tables. For screening and baseline visits, the last assessment value will be used. All the recorded data will be listed. If observations have the same distance to the scheduled assessment, the latest one will be used.

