Symptoms and Signs	Symptoms Subcategories	TOL-463 Vaginal Insert (N=X)					Placebo (N=X)					All Subjects (N=X)				
		Visit 0	Visit 1	Visit 2	Visit 3	Visit 4	Visit 0	Visit 1	Visit 2	Visit 3	Visit 4	Visit 0	Visit 1	Visit 2	Visit 3	Visit 4
Abnormal Vaginal Discharge	n	n	n	n	n	n	n	n	n	n	n	n	n	n	n	n
	No	x	x	x	x	x	x	x	x	x	x	x	x	x	x	x
	Yes, consistent with BV	x	x	x	x	x	x	x	x	x	x	x	x	x	x	x
	Yes, other	x	x	x	x	x	x	x	x	x	x	x	x	x	x	x
Vaginal Odor	n	n	n	n	n	n	n	n	n	n	n	n	n	n	n	n
	No	x	x	x	x	x	x	x	x	x	x	x	x	x	x	x
	Yes, consistent with BV	x	x	x	x	x	x	x	x	x	x	x	x	x	x	x
	Yes, other	x	x	x	x	x	x	x	x	x	x	x	x	x	x	x

Notes: N=Number of subjects in the mITT population in the specified group.

Subjects will be further excluded if no data is available at the specified timepoint, n=Number of subjects with available data for the specified category at the specified timepoint, and these counts are shown in the row of n, whereas the data shown in the rows of each response level in this table are percentages, where n is the denominator.

For post-enrollment visits, observations from early termination at an unscheduled visit will be summarized into the preceding scheduled visit. For Vaginal Discharge and Odor responses from the scheduled visit and the corresponding unscheduled early termination visit, count the subject in “Yes, consistent with BV” when at least one response was “Yes, consistent with BV”; count the subject in “Yes, other” when no response was in “Yes, consistent with BV” and at least one response was from “Yes, other”; count the subject in “No” when all responses were “No”.

Table 16: Summary of Proportion of Participants Reporting BV Symptoms – PP Population

Symptoms and Signs	Subcategories	TOL-463 Vaginal Insert (N=X)					Placebo (N=X)					All Subjects (N=X)				
		Visit 0	Visit 1	Visit 2	Visit 3	Visit 4	Visit 0	Visit 1	Visit 2	Visit 3	Visit 4	Visit 0	Visit 1	Visit 2	Visit 3	Visit 4
Abnormal Vaginal Discharge	n	n	n	n	n	n	n	n	n	n	n	n	n	n	n	n
	No	x	x	x	x	x	x	x	x	x	x	x	x	x	x	x
	Yes, consistent with BV	x	x	x	x	x	x	x	x	x	x	x	x	x	x	x
	Yes, other	x	x	x	x	x	x	x	x	x	x	x	x	x	x	x
Vaginal Odor	n	n	n	n	n	n	n	n	n	n	n	n	n	n	n	n
	No	x	x	x	x	x	x	x	x	x	x	x	x	x	x	x
	Yes, consistent with BV	x	x	x	x	x	x	x	x	x	x	x	x	x	x	x
	Yes, other	x	x	x	x	x	x	x	x	x	x	x	x	x	x	x

Notes: N=Number of subjects in the PP population in the specified group.

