Symptoms/Signs Severity	TOL-463 Vaginal Insert (N=X)					Placebo (N=X)					All Subjects (N=X)				
	Visit 0	Visit 1	Visit 2	Visit 3	Visit 4	Visit 0	Visit 1	Visit 2	Visit 3	Visit 4	Visit 0	Visit 1	Visit 2	Visit 3	Visit 4
Erythema															
n	n	n	n	n	n	n	n	n	n	n	n	n	n	n	n
Absent	x	x	x	x	x	x	x	x	x	x	x	x	x	x	x
Mild	x	x	x	x	x	x	x	x	x	x	x	x	x	x	x
Moderate	x	x	x	x	x	x	x	x	x	x	x	x	x	x	x
Severe	x	x	x	x	x	x	x	x	x	x	x	x	x	x	x
Excoriation															
n	n	n	n	n	n	n	n	n	n	n	n	n	n	n	n
Absent	x	x	x	x	x	x	x	x	x	x	x	x	x	x	x
Mild	x	x	x	x	x	x	x	x	x	x	x	x	x	x	x
Moderate	x	x	x	x	x	x	x	x	x	x	x	x	x	x	x
Severe	x	x	x	x	x	x	x	x	x	x	x	x	x	x	x
KOH Wet Mount Microscopy: Yeast (budding, branching, hyphae)															
n	n	n	n	n	n	n	n	n	n	n	n	n	n	n	n
Absent	x	x	x	x	x	x	x	x	x	x	x	x	x	x	x
Present	x	x	x	x	x	x	x	x	x	x	x	x	x	x	x
Clinical Diagnosis of Vulvovaginal Candidiasis															
n	N/A	n	n	n	n	N/A	n	n	n	N/A	n	n	n	n	n
Yes	N/A	x	x	x	x	N/A	x	x	x	N/A	x	x	x	x	x
No	N/A	x	x	x	x	N/A	x	x	x	N/A	x	x	x	x	x
Culture Confirmed Vulvovaginal Candidiasis															
n	N/A	n	n	n	n	N/A	n	n	n	N/A	n	n	n	n	n
Yes	N/A	x	x	x	x	N/A	x	x	x	N/A	x	x	x	x	x
No	N/A	x	x	x	x	N/A	x	x	x	N/A	x	x	x	x	x

Symptoms/Signs Severity	TOL-463 Vaginal Insert (N=X)					Placebo (N=X)					All Subjects (N=X)				
	Visit 0	Visit 1	Visit 2	Visit 3	Visit 4	Visit 0	Visit 1	Visit 2	Visit 3	Visit 4	Visit 0	Visit 1	Visit 2	Visit 3	Visit 4

Notes: N=Number of subjects in the Safety population in the specified group.

Subjects will be further excluded if no data is available at the specified timepoint, n=Number of subjects with available data for the specified category at the specified timepoint, and these counts are shown in the row of n, whereas the data shown in the rows of each response level in this table are percentages, where n is the denominator.

Observations from early termination at an unscheduled visit will be summarized into the preceding scheduled visit. For Burning, Irritation, Itching, Edema, Erythema, and Excoriation, the maximum severity level from the scheduled visit and the corresponding unscheduled early termination visit will be counted. For KOH wet mount Microcopy responses from the scheduled visit and the corresponding unscheduled early termination visit, count the subject in "Present" when at least one response was "Present", and count "Absent" when all responses were "Absent".

Table 38: Additional Pelvic Examination Measures

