TOL-463 Vaginal Insert /Placebo	xxxxxx	xx	xxxxxxxx	xxxxxxxx	xx	xxxxxxxx	Yes/No	Yes/No	Yes/No	Yes/No	xxxxxxxx

Listing 5: Non-Subject-Specific Protocol Deviations

Implementation Notes:

1. Sort order will be by Site, Start Day.
2. In the Deviation Description column concatenate any specify fields.
3. In the Reason for Deviation column concatenate any specify fields.

Site	Start Date	Deviation Description	End Date	Reason for Deviation	Deviation Resulted in Subject Termination?	Deviation Affected Product Stability?	Deviation Category	Deviation Resolution	Comments
xxxx	ddMMMyyyy	xxxx	ddMMMyyyy	xxxx	Yes/No	Yes/No	xx	xxxx	xxxxxxxx
xxxx	ddMMMyyyy	xxxx	ddMMMyyyy	xxxx	Yes/No	Yes/No	xx	Xxxx	xxxxxxxx

Listing 6: Amsel Criteria and Nugent Score for BV

[Implementation notes: Continue for all subjects. List any unscheduled visit (should be for a termination visit), if exist.]

Subject ID	Treatment Group	Visit	Study Day	Amine ("whiff") test on KOH wet mount	Homogeneous Vaginal discharge characteristic of BV	Clue cells > or = 20% of the total vaginal squamous epithelial cells on saline microscopy (%)	Vaginal pH	Presence of Amsel Criteria	Clinical Diagnosis of BV	Nugent Score	BD Max BV Result
xxxxxx	TOL-463 Vaginal Insert/Placebo	00	-xx	Positive/Negative/Not Assessed	Yes/No/Not Assesses	Present/Absent/Not Assessed	xx.x/Not Assessed	0/1/2/3/4	Positive/Negative	x	Positive/Negative
		01	xx	Positive/Negative/Not Assessed	Yes/No/Not Assesses	Present/Absent/Not Assessed	xx.x/Not Assessed	0/1/2/3/4	Positive/Negative	x	Positive/Negative
		02	xx	Positive/Negative/Not Assessed	Yes/No/Not Assesses	Present/Absent/Not Assessed	xx.x/Not Assessed	0/1/2/3/4	Positive/Negative	x	Positive/Negative
		03	xx	Positive/Negative/Not Assessed	Yes/No/Not Assesses	Present/Absent/Not Assessed	xx.x/Not Assessed	0/1/2/3/4	Positive/Negative	x	Positive/Negative
		04	xx	Positive/Negative/Not Assessed	Yes/No/Not Assesses	Present/Absent/Not Assessed	xx.x/Not Assessed	0/1/2/3/4	Positive/Negative	x	Positive/Negative

Notes: Clinical diagnosis of BV is based on the presence of Amsel criteria (Positive when Amsel criteria >2). Vaginal pH > 4.5 will meet the pH criterion.

Listing 7: Individual Time to Recurrent Bacterial Vaginosis (RBV)

Subject ID	Treatment Group	Clinical Diagnosis of BV by Visit 4 [Window: Day 85-91]	Time to RBV Definition 1 ^a	Time to RBV Definition 2 ^b	Time to RBV Definition 3 ^c
xxxxxx	TOL-463 Vaginal Insert/Placebo	Positive/Negative	x	x/N/A	x/N/A

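### BV symptoms at unscheduled visits that do not end participation have no stated place in SAP Tables 15 and 16, and those at a termination before V2 are dropped or put in the baseline column, so Secondary Endpoint 2 can be understated

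*SAP*

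**What the plan says.** **Unscheduled visits are expected and need not end participation.** Protocol 5 states: "Participants who develop vaginal symptoms between scheduled visits will be asked to return for an unscheduled visit". Under Protocol 6.4, a woman found at such a visit to have 2 or fewer Amsel criteria "will be scheduled for the next return visit, blinded IP and a memory aid will be provided as needed". Protocol 7.1.1 adds that "participants who have received study IP and are subsequently diagnosed with VVC can remain in the study and be considered evaluable for efficacy", provided that oral fluconazole is suitable.

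**The tables use only terminating unscheduled visits.**
- Table 15 (BV symptoms, mITT): "For post-enrollment visits, observations from early termination at an unscheduled visit will be summarized into the preceding scheduled visit". A worst-of rule for combining the two readings follows.
- Table 16 (the same table in the PP population): no rule for unscheduled visits.
- Table 37 (vulvovaginal signs and symptoms, yeast, VVC): "Observations from early termination at an unscheduled visit will be summarized into the preceding scheduled visit". A worst-of rule is given for the six signs and symptoms and for KOH microscopy, but not for the clinical or culture-confirmed VVC rows.
- Listing 6: "List any unscheduled visit (should be for a termination visit), if exist".

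**The general rule is in SAP 4.5.** When a window holds several observations, "the assessment value that is closest to the scheduled visit window will be used in the analyses for the post-baseline records". The same section leaves the handling of terminations at unscheduled visits to the individual tables.

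**The endpoint is cumulative.** SAP 3.2.2 defines Secondary Endpoint 2 as the proportion reporting BV symptoms over follow-up as a whole. SAP 8.2 estimates it at each visit, in Tables 15 and 16.

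**The concern.** The Listing 6 note treats an unscheduled visit as a termination visit, and the table notes follow the same pattern. The protocol does not. A woman who comes back because of symptoms, does not meet the recurrence definition and stays in the trial is an ordinary case, yet no table note says where her reading goes. Because these visits are prompted by symptoms, the readings without a place are likely to be mostly positive ones.

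The matter is sharper because of the source of the data. Protocol 10.5.4.2 takes symptoms from the daily memory aid, which covers the time between visits. The SAP's analysis text and table shells do not carry that source forward. Unscheduled visits are then the main remaining record of symptoms between scheduled visits. At stake is a descriptive secondary endpoint, together with the by-visit picture of VVC in Table 37.

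**Working it through.** The plan states no figure that depends on this point, so the check sets the rules against three constructed records.

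**Inputs.** Follow-up windows are Days 29-35, 57-63 and 85-91 (Protocol Appendix A). Between Day 2 and Day 91 there are 90 days. The days outside every window are 2-28, 36-56 and 64-84, that is 27 + 21 + 21 = 69. Most between-visit readings would therefore fall outside any window.

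**Record A: symptoms, continues.** V2 and V3 take place in window without symptoms. At an unscheduled visit on Day 45 she reports discharge and odor consistent with BV, has 2 Amsel criteria and continues. V4 is clear.
- The Table 15 note does not apply, because the visit was not a termination.
- Under SAP 4.5, the Day 45 reading lies 45 − 35 = 10 days after the V2 window and 57 − 45 = 12 days before the V3 window. Each in-window scheduled reading has distance 0 and is kept.
- She counts as having no symptoms in all three follow-up columns, although the endpoint should count her.

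**Record B: termination before V2.** On Day 18 she is symptomatic, has 4 Amsel criteria and is terminated.
- Her preceding scheduled visit is V1.
- If the opening words of the Table 15 note limit which columns can receive a reading, hers goes nowhere. If they describe when the reading was taken, it goes into the V1 column.
- Absence of BV symptoms is an entry criterion at V1 (Protocol 5.1.1.2), so neither outcome shows an on-treatment symptom.
- The Table 37 note has no such opening words and puts her vulvovaginal findings in V1.

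**Record C: VVC, continues.** VVC is found and treated on Day 45, and she is clear at V3.
- Table 37 has no stated place for the Day 45 finding.
- If it is culture-confirmed, she does count in Table 36, which counts subjects from start of treatment to final visit and has no visit columns.

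**Analyses not affected.** More than 2 Amsel criteria at an unscheduled visit meets the recurrence endpoint and ends participation (Protocol 5 and 6.4). SAP 8.2 includes recurrence diagnosed at unscheduled visits in the time-to-event analysis.

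**Size.** Let *s* be the proportion of women with symptoms at readings the tables use, and *u* the further proportion with symptoms only at readings they do not. The relative undercount of a cumulative proportion is *u* / (*s* + *u*). The documents give neither value. Purely as assumptions, *s* from 10% to 30% and *u* from 2% to 10% give a range from 2 / (30 + 2) = 6% to 10 / (10 + 10) = 50%. This illustrates how little can be said and is not an estimate.

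**The case against.** The strongest reply is that this is unclear wording, not demonstrated loss. SAP 4.5 is not limited to terminating visits and does not define its visit period. The abbreviation list labels V2 as weeks 1-4, so a programmer could place a Day 18 reading under V2. A non-terminating reading could also be used if it were the only or closest one. SAP 4.5 promises that all recorded data will be listed. The endpoint is descriptive, and unscheduled-visit assessments are at the site investigator's discretion, so some readings will not exist.

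Part of this stands. The consequence is confined to descriptive tables, and the SAP does not order deletion in so many words. But SAP 4.5 sends terminations at unscheduled visits to the table notes, and those point backward to the preceding visit. Where both neighbouring visits took place in window, the closest-value rule discards the reading between them. The shells of Listings 8 and 19 have an early-termination row but none for other unscheduled visits, which sits poorly with the promise to list everything.

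A reader might infer three stronger things that the documents do not support:
- **VVC found at unscheduled visits is lost.** It is not lost from Secondary Endpoint 5. Protocol 6.4 provides for Candida culture at these visits, and Table 36 counts the result. Only the by-visit Table 37 can miss it.
- **Table 15 has no column for a termination before V2.** It has a Visit 1 column. The defect is that this is a baseline column and that the note is ambiguous about using it.
- **The treatment difference is diluted.** The design's 40% and 20% recurrence rates suggest more early terminations on placebo. A shrunken difference follows only if timing and detection are alike in both arms, which nothing in the documents establishes. For non-terminating visits the direction is unknown.

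**Conclusion.** The concern holds for BV symptoms. Symptoms at non-terminating unscheduled visits have no stated place in Tables 15 and 16. Symptoms at a termination before V2 are, on the Table 15 note, either omitted or shown at baseline, and the Table 37 note puts vulvovaginal findings from such a visit at baseline. By-visit columns alone cannot yield a proportion defined over all of follow-up, so Secondary Endpoint 2 can be understated. For VVC the gap is limited to the descriptive Table 37.

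The size of the undercount and any effect on the comparison between arms are unknown. The conclusion rests on the wording of the rules and on the protocol allowing women to continue, not on any assumed visit frequency. It should be corrected, because a defined secondary endpoint is not reported as defined and the remedy is cheap.

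**What to change.** 1. **SAP 4.5 and the notes to Tables 15, 16 and 37.** Use all available unscheduled readings after Day 1, terminating or not. Assign each to the scheduled visit that closes its interval; anything after Day 1 and before V2 goes to V2, never V1. Combine it with the scheduled reading by the worst-of rule in Table 15, and write that rule out for Table 16 and for the clinical and culture-confirmed VVC rows of Table 37. If the closing visit did not take place, the unscheduled reading is the value. State that the closest-to-window rule does not apply to these variables.
2. **Tables 15 and 16.** Add a subject-level row by arm, *any BV symptom after first dose through last visit*, using all visits, to match the endpoint in SAP 3.2.2.
3. **Listings.** Remove the parenthesis in the Listing 6 note that presumes termination. Add unscheduled-visit rows to Listings 8 and 19.

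The cost is SAP wording and a modest amount of programming, with no new data collection. One small downside is that the by-visit columns become interval summaries instead of pure visit prevalence; the footnotes should say so.
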